
 To evaluate additional safety and tolerability measures 	
 Number of subjects who discontinued due to TEAEs and due to related TEAEs Incidence and shifts of clinically significant physical examination findings, ECG data and laboratory abnormalities; safety laboratory evaluations include hematology, blood biochemistry and urinalysis, serum, salivary, and urinary cortisol as appropriate Change from baseline in 
 IGF-1

Objectives	Endpoints
	
– Bone biomarkers: CTX, P1NP and osteocalcin– TSH• Absolute and % change from baseline in lumbar spine, total hip, and femoral neck BMD as assessed by DXA

• To evaluate the immunogenicity of pegozafermin over time	
• Incidence and characteristics of ADA and NAb after dosing (e.g., titer and binding specificity, to the FGF21 and PEG part of pegozafermin)• Impact of the presence of ADAs on serum pegozafermin concentrations and clinical safety• Levels of endogenous FGF21 at immunogenicity follow-up visit(s) compared to baseline in [REDACTED] subjects

Overall Design

This is a randomized, double-blind, placebo-controlled, 2-part study to evaluate efficacy, safety, tolerability, population PK and pharmacodynamic (PD) profiles and immunogenicity of pegozafermin administered subcutaneously (SC) in approximately 184 subjects with biopsy-confirmed NASH (NAS \geq 4, fibrosis stage F2 or F3 per NASH Clinical Research Network (CRN) system). The first part of the study will be double-blind, and the second part of the study will be single-blind (specifically-identified Sponsor personnel will not be blinded). Study schema is shown in Section 1.2.

The study will include 2 parts:

- Main study – a 24-week, double-blind, placebo-controlled study
- Extension study – an additional 24-week, single-blind, placebo-controlled study

The entire study will include a Screening period, a Treatment period (Main and Extension), and a Follow-up period. Study visits and assessments will be conducted in-clinic and/or remotely as shown in the schedule of activities (SoA) in Section 1.3 and described in Section 4.1.

Throughout the study (Main and Extension), subjects will be evaluated as specified in the SoA. All subjects will be followed-up for at least 4 weeks after last dose of investigational product (IP).

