1.2. Study Schema

Figure 1: BIO89-100-122 Study Schema

Abbreviations: EOS, end of study; QW, weekly; Q2W, every other week; R, At Week 24, subjects randomized to placebo QW in the Main study will be re-randomized 1:1 to pegozafermin 30 mg (n=21) or placebo QW (n=21)

Notes: The 12-week screening period may be extended with Sponsor's approval. Subjects, investigators and site staff and Sponsor will be blinded to investigational product (placebo or pegozafermin) in the Main study. During the Extension study, the Medical Monitor will remain blinded to treatment assignment. Designated members of the unblinded team are specified in the Sponsor Unblinding Plan. Subjects, investigators, and site staff will remain blinded to IP. However, the dose regimen (QW or Q2W) will be known to all parties involved in both the Main and Extension study.

Subject assigned to placebo QW in the Main study will be re-randomized 1:1 to pegozafermin 30 mg QW or placebo QW at the Week 24 visits and will receive the re-randomized treatment at the Week 26 visit.

Treatment duration for Main Study includes 24 administrations in QW dose regimen and 12 administrations in Q2W dose regimen + 1 week for evaluation of endpoints (Week 24); treatment duration for Extension includes 24 administrations in QW dose regimen and 12 administrations in Q2W dose regimen + 1 week for evaluation of endpoints (Week 48).

The study includes an immunogenicity follow-up period of up to [REDACTED] with follow-up visits approximately every 12 weeks after the Week 48 visit.
Abbreviations: EOS, end of study; QW, weekly; Q2W, every 2 weeks, R, randomization.

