1.3. Schedule of Activities (SoA)

Table 1: Schedule of Activities

Subjects will attend clinic visits for Screening, Baseline (Day 1), Week 4, Week 12, Week 24, Week 38 and Week 48/ET.

Assessments	Screening Period ¹	Treatment Period										FU Period	Notes:
		Main Study					Extension Study						
Study Day		1 ²											
Study Weeks	-12 to 0		4 ³	8 ⁴	12 ³	16 ⁴	24 ³	26 ⁵	30 ⁴	38 ³	48 ³	ET ^{3,6}	51 ^{7/} EOS
Visit window (days)			±2	±7	±7	±7	+7	+7	±7	±14	+14		±14
Informed consent	X												
Medical history/ demographics	X												
Liver biopsy	X ^a						X ^b				X ^c		Liver biopsies should ideally be done after MRI-PDFF. a. Must meet study inclusion criteria. A biopsy performed within 6 months of screening is acceptable instead of the baseline liver biopsy if the sample is deemed interpretable and eligible by the central reader. b. To be performed at -7 to +14 days of the Week 24 target visit; if biopsy not performed by Week 26 for subjects in QW groups, W26 dose to be held until discussion with Sponsor c. Applicable for subjects who discontinue IP at or after Week 16 and before Week 24 of the Main study.
Histology machine read (PathAI)	X					X					X ^c		c. Applicable for subjects who discontinue IP at or after Week 16 and before Week 24 of the Main study.
Prior medications	X												
Inclusion and exclusion criteria	X	B											

Assessments	Screening Period ¹	Treatment Period										FU Period	Notes:
		Main Study					Extension Study						
Study Day		1 ²											
Study Weeks	-12 to 0		4 ³	8 ⁴	12 ³	16 ⁴	24 ³	26 ⁵	30 ⁴	38 ³	48 ³	ET ^{3,6}	51 ⁷ /EOS
Visit window (days)			±2	±7	±7	±7	+7	+7	±7	±14	+14		±14
Complete physical exam	X ^d					X			X				d. includes recording height, weight, and calculating BMI.
Limited physical assessment ^e		B	X	X	X	X		X	X		X		e. if clinically indicated. May be performed by home health nurse for remote visits.
Body weight	X	B		X		X			X	X	X		The Investigator will be requested to further evaluate subjects with weight loss of $\geq 15.0\%$ at Week 12 and $\geq 20.0\%$ at Week 24, from baseline, for the potential cause of weight loss.
Waist and hip circumference	X	X		X		X			X	X	X		
Lifestyle counseling	X	X	X	X	X	X	X	X	X				Strenuous exercises should be avoided for at least 48 hours prior to study visits.

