4.3. Justification for Dose

The dose levels and regimens for this study, pegozafermin QW (15 mg or 30 mg) or Q2W (44 mg), were selected based on nonclinical safety and pharmacology studies in mice and monkeys, safety and pharmacodynamic data from the single ascending dose (SAD) study TV47948-SAD-10122, and data from the multiple ascending dose (MAD) study BIO89-100-002 Part 1.

In Part 1 of Study BIO89-100-002, exposures to pegozafermin (ascending doses 3 mg, 9 mg, 18 mg, and 27 mg QW and 18 mg and 36 mg Q2W) in subjects with NASH and PNASH for up to 12 weeks were generally dose-proportional following QW or Q2W dosing. Exposures were related to the total doses regardless of dosing regimens. Terminal phases of concentration-time profiles were parallel, suggesting a dose-proportional PK. AUC_{last} values stratified by regimens are also generally dose-proportional. Group t_{max} occurred between 48 and 72 hours after dosing. Accumulation ratios ranged from 1.0 to 1.4.

Exposure-response relationship based on Week [REDACTED] was established using data from Study BIO89-100-002 (Part 1). The data show that higher exposures were associated with better response and can be described by an E_{max} (maximum effect) model. The high dose proposed for this study, 30 mg QW, likely approaches full effect. The proposed low dose, 15 mg QW, is expected to elicit close to or slightly better than EC50 effect. The 44 mg Q2W dose (roughly equivalent to 22 mg, QW) is proposed as a middle dose.

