4.4. Study Duration

For each subject, the total duration of study participation will be up to approximately 112 weeks:

Screening Period:	Up to 12 weeks, which may be extended with Sponsor's approval
Main Study	24 weeks (includes 24 administrations in QW dose regimen and
Treatment Period:	12 administrations in Q2W dose regimen)
Extension Study	24 weeks (includes 24 administrations in QW dose regimen and
Treatment Period	12 administrations in Q2W dose regimen)
Extension Study	Approximately 4 weeks from last dose of IP
Follow-up Period	
Immunogenicity	Approximately [REDACTED] from last dose of IP
Follow-up Period	

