6.2. Analysis Visit Windows

In general, scheduled visits from randomization (except for early terminated subjects) will be used as analysis visit for descriptive analysis tables and listings. Unscheduled visits, ET visit, and EOS visit will be mapped according to the actual study day and analysis visit window defined in [Table 4](#).

Scheduled visit will be selected for analysis/summaries if has valid assessment result. If a scheduled visit is missing, the unscheduled visit that is closest to the target study day will be used for analysis purpose.

Table 4: General Analysis Visit Window

Study Period	Target Study Weeks	Target Study Day	Analysis Visit Window (Days)
Screening Period	-12 to 0	--	--
Main Study	--	1	--
	4	29	2 to 43
	8	57	44 to 71
	12	85	72 to 99
	16	113	100 to 141
	24	169	142 to min (the date all Week 24 assessments completed, Main Study cut-off date)
Extension Study	26	183	•
	30	211	(W24 End date+1) to 239
	38	267	240 to 302
	48	337	303 to 351
Follow-up Period	ET	--	--
	51/EOS	358	>= 352

Week 26 is the start visit for the extension study dosing, no need to be included in the visit-based summary tables if no data is collected.

For parameters with scheduled visit(s) at Week 12 and Week 24, or Week 24 only, the analysis window will be adjusted such that:

- The first post-baseline scheduled visit will start at day 2. Other visits start from the end of previous visit + 1 day.
- The end of each analysis visit window will be middle to the next scheduled visit (If an even number of days exists between two consecutive visits then the end date will be taken as the midpoint value minus 1 day).

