			Q2W from Weeks 2 to 22		Q2W from Weeks 24 to 46								n. IP will be administered SC to the abdomen by trained and qualified study personnel, site staff at clinic visit(s), or at home by healthcare professional, or subject's caregiver for home administration. IP may also be self-administered at the subject's home.	
													o. Week 26 may be an in-clinic or a remote/home visit by healthcare professional who will administer the IP.	
PK blood collection ^p		B	B	B	B		B			B	X	X		p. PK blood samples will be collected predose. Additional blood samples for PK analysis may be collected if clinically indicated (e.g., in case of SAE). For PK sample collection instruction/procedures, refer to the relevant manual.

Assessments	Screening Period ¹	Treatment Period										FU Period	Notes:
		Main Study					Extension Study						
Study Day		1 ²											
Study Weeks	-12 to 0		4 ³	8 ⁴	12 ³	16 ⁴	24 ³	26 ⁵	30 ⁴	38 ³	48 ³	ET ^{3,6}	51 ⁷ /EOS
Visit window (days)			±2	±7	±7	±7	±7	+7	±7	±14	+14		±14
ELF panel, Pro-C3, adiponectin, FIB-4 index (derived calculation), and adipo-IR (fasting free fatty acids x fasting insulin)		B		X		X			X	X	X		Refer to Appendix 2 (Section 10.2).
Night-time salivary cortisol (NSC) ^q	X ^q			X	X			X	X	X			q. NSC sample will be collected by subject at home between 8:00pm and 12:00am before submitting the sample for processing at the specified visit. If the sample is not collected between 8:00pm and 12:00am, the test should be repeated. The screening assessment should be performed as early as possible during the screening period. Subjects should be provided with NSC collection kit at the first screening visit, when possible, to allow sample collection return at the following clinic visit. If screening value is >15 nmol/L, Medical Monitor (or designee) may request further workup should the value be of clinical concern; however, values >15 nmol/L will not be exclusionary. The screening NSC is a safety assessment, and not an I/E criteria. Refer to Section 10.2 for further requirement for Value >15 nmol/L on treatme

Assessments	Screening Period ¹	Treatment Period										FU Period	Notes:
		Main Study					Extension Study						
Study Day		1 ²											
Study Weeks	-12 to 0		4 ³	8 ⁴	12 ³	16 ⁴	24 ³	26 ⁵	30 ⁴	38 ³	48 ³	ET ^{3,6}	51 ⁷ /EOS
Visit window (days)			±2	±7	±7	±7	±7	+7	±7	±14	+14		±14

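### Week 48 and EOS visits are not tied to the last dose, so late Week 48 samples can count as troughs and an early EOS visit falls short of four weeks' follow-up

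*Protocol*

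**What the plan says.** **Dosing.** The notes in Protocol 1.2 say that "treatment duration for Extension includes 24 administrations in QW dose regimen", and for the other regimen "12 administrations in Q2W dose regimen + 1 week for evaluation of endpoints (Week 48". The schedule of activities places the last QW dose at Week 47. For the other regimen, SAP Appendix 1 has "Q2W from Weeks 24 to 46".

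**Windows.** In Protocol 1.3, the row "Visit window (days" gives +14 for Week 48 and ±14 for Week 51/EOS. One page of the schedule in SAP Appendix 1 prints Week 48 as ±14 instead.

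**Follow-up.** Protocol 1.1 states: "All subjects will be followed-up for at least 4 weeks after last dose of investigational product (IP". SAP 3.1 repeats this minimum. Protocol 4.4 (and the duration part of 1.1) is looser: "Approximately 4 weeks from last dose of IP".

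**Analysis.** SAP 6.2 uses a scheduled visit whenever it has a valid result. It adds: "Unscheduled visits, ET visit, and EOS visit will be mapped according to the actual study day and analysis visit window". Table 4 there runs Week 48 from Day 303 to Day 351 and starts EOS at Day 352. SAP 7.11 summarises serum concentration by timepoint, with no condition on time since the last dose. Trough concentration and the Week 48 changes in MRI-PDFF, ALT and Pro-C3 are the Extension's secondary endpoints.

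**The concern.** No dose is scheduled at or after Week 48. A visit that runs late is therefore a visit further off drug, with no later dose to restore exposure. The trough endpoint suffers most directly: a concentration taken well past the end of a dosing interval is not a trough, yet it would be averaged with those that are. ALT and Pro-C3 could also drift back toward untreated values. A reader of the final tables could take either change for waning exposure or effect.

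At the other end, an EOS visit on its earliest permitted day does not deliver the stated minimum follow-up. Because EOS visits are mapped by actual day, such a visit can also be labelled Week 48.

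**Working it through.** **Inputs.** SAP Table 4 puts Week 48 at Day 337 and Week 51/EOS at Day 358, so day = 7 × week + 1. Last doses: 7 × 47 + 1 = Day 330 (QW) and 7 × 46 + 1 = Day 323 (Q2W). Windows in Protocol 1.3: Week 48 on Days 337 to 337 + 14 = 351; EOS on Days 358 − 14 = 344 to 358 + 14 = 372.

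**Step 1: the plan's own figures at planned dates.** QW: 337 − 330 = 7 days and 358 − 330 = 28 days, which reproduces both the one week and the four weeks. Q2W: 337 − 323 = 14 days and 358 − 323 = 35 days. The schema's one week is therefore not reproduced for Q2W even when every visit is on time.

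**Step 2: days since last dose at the window limits.**

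| Visit | QW | Q2W |
|---|---|---|
| Week 48, planned | 7 | 14 |
| Week 48, latest (Day 351) | 351 − 330 = 21 | 351 − 323 = 28 |
| EOS, earliest (Day 344) | 344 − 330 = 14 | 344 − 323 = 21 |
| EOS, planned | 28 | 35 |
| EOS, latest (Day 372) | 42 | 49 |

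**Step 3: share of EOS days that give at least 28 days.** The window has 29 days. QW needs Day 358 or later: 15 of 29. Q2W needs Day 351 or later (323 + 28): 22 of 29.

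**Step 4: overlap.** The two visit windows share Days 344 to 351. Table 4 assigns those days to Week 48, so an EOS visit there maps to Week 48 and can fill in for a missing scheduled visit. This matters only for measurements taken at EOS. The biochemistry row, which includes ALT, appears to reach that visit, but the row layout is broken in the text read here.

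**Step 5: rough size for the trough.** Protocol 4.3 reports: "Accumulation ratios ranged from 1.0 to 1.4". Assume one-compartment decay, with accumulation ratio R = 1/(1 − e^(−kτ)) for dosing interval τ. Then e^(−kτ) = 1 − 1/R, which is 1 − 1/1.4 = 0.286 at the highest ratio. At Week 48 + 14 days both regimens are 14 days past the usual end of interval.
- If 1.4 describes QW (τ = 7), 14 days is two intervals: 0.286² = 0.082, about 8% of trough.
- If 1.4 describes Q2W (τ = 14), 14 days is one interval: 0.286, about 29% of trough.

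Smaller ratios give lower values, falling to zero as R approaches 1.0. The protocol does not say which regimen the ratio belongs to. If one half-life served both regimens, the remaining fraction at equal lateness would be the same, and the regimens would differ in absolute concentration because their troughs differ.

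For a share p of samples 14 days late with remaining fraction f, the mean becomes 1 − p(1 − f) of the true trough. The documents give no p.

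**The case against.** The strongest reply is that these are limits, not expectations. On planned dates Week 48 falls exactly one dosing interval after the last dose in both regimens, and EOS gives 28 or 35 days. That stands. A reader might infer that Week 48 values are typically taken 21 to 28 days off drug; those are single latest days, one per regimen.

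Other stronger readings also fail:
- **Week 24 and Week 48 cannot be compared.** Main Study dosing ends at Week 23 (QW) or Week 22 (Q2W), so planned Week 24 is also 7 or 14 days after the previous dose. No test between the two visits is planned; SAP 7.12.2 compares arms with placebo.
- **An early EOS visit contradicts the 28-day adverse event period.** Protocol 8.3.1 defines that period in days, not by the visit. Subjects who complete Week 48 also have events collected from Week 60.
- **Antibody samples are taken too early at EOS.** The schedule row, as read here, does not establish that any are taken then.
- **Table 4's upper limit lets late scheduled visits in.** A valid scheduled Week 48 result is used under its own label, so changing Day 351 would not exclude it.

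MRI-PDFF has its own target of ±7 days, which limits its lateness, though the wording is only advisory.

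Two defences are weaker. The PK Analysis Set asks for data adequate to characterise troughs, but it selects subjects rather than samples, and a visit inside its window is no violation. The schedule codes Week 48 PK differently from the predose visits, but SAP 7.11 does not use that distinction. That every arm shares the window also gives only partial comfort: placebo has no drug effect to lose, so late visits would shrink a difference rather than cancel out.

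Finally, footnotes 3, 6 and 7 in the schedule's column headings are not in the text read here. A rule linking Week 48 or EOS to the last dose cannot be excluded.

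**Conclusion.** The point holds as a gap in the analysis rules and a conflict between passages. The windows permit Week 48 up to 21 (QW) or 28 (Q2W) days after the last dose, and EOS as early as 14 or 21 days. The second conflicts with the stated minimum of four weeks, and the documents also disagree on whether four weeks is a minimum or an approximation.

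Late Week 48 samples bias the trough endpoint downward. At the 14-day limit a sample holds roughly 8% or 29% of trough at most, given one-compartment decay and a ratio of 1.4; this is an order of magnitude for a subcutaneous drug, not an estimate. The absolute loss differs between regimens. The overall bias depends on how many visits are late, which is unknown. ALT and Pro-C3 may be affected to a degree the documents do not let anyone quantify, and MRI-PDFF less so.

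The Main Study primary endpoints are not touched. The Extension's adverse event endpoint is not diluted in this way. The missing footnotes could remove the visit-timing part, especially for EOS.

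**What to change.** 1. **SAP 7.11:** admit a sample to the trough summary only if it was taken at about the end of one dosing interval after the last recorded dose, for example 7 ± 2 days (QW) or 14 ± 2 days (Q2W). List the others with their time since dose.
2. **SAP 7.12.2:** add a supportive Week 48 analysis of ALT, Pro-C3 and MRI-PDFF limited to assessments within a pre-stated time since last dose.
3. **SAP 6.2:** state that an EOS visit is not mapped to Week 48.
4. **Reconcile** the minimum follow-up (Protocol 1.1, SAP 3.1) with the approximate one (Protocol 1.1 and 4.4), the schema's one week, the Week 48 and EOS windows (including the ±14 printed in SAP Appendix 1) and Table 4. The choice of schedule is the sponsor's.

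**Cost.** A few SAP sentences and one extra analysis. Some PK samples leave the trough summary: under the example limits, Days 337 to 339 qualify, 3 of the 15 permitted days in either regimen. The loss is small if visits cluster at the target date and larger if they spread across the window.

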1.3. Schedule of Activities (SoA)

Table 1: Schedule of Activities

Subjects will attend clinic visits for Screening, Baseline (Day 1), Week 4, Week 12, Week 24, Week 38 and Week 48/ET.

Assessments	Screening Period ¹	Treatment Period										FU Period	Notes:
		Main Study					Extension Study						
Study Day		1 ²											
Study Weeks	-12 to 0		4 ³	8 ⁴	12 ³	16 ⁴	24 ³	26 ⁵	30 ⁴	38 ³	48 ³	ET ^{3,6}	51 ^{7/} EOS
Visit window (days)			±2	±7	±7	±7	+7	+7	±7	±14	+14		±14
Informed consent	X												
Medical history/ demographics	X												
Liver biopsy	X ^a						X ^b				X ^c		Liver biopsies should ideally be done after MRI-PDFF. a. Must meet study inclusion criteria. A biopsy performed within 6 months of screening is acceptable instead of the baseline liver biopsy if the sample is deemed interpretable and eligible by the central reader. b. To be performed at -7 to +14 days of the Week 24 target visit; if biopsy not performed by Week 26 for subjects in QW groups, W26 dose to be held until discussion with Sponsor c. Applicable for subjects who discontinue IP at or after Week 16 and before Week 24 of the Main study.
Histology machine read (PathAI)	X					X					X ^c		c. Applicable for subjects who discontinue IP at or after Week 16 and before Week 24 of the Main study.
Prior medications	X												
Inclusion and exclusion criteria	X	B											

Assessments	Screening Period ¹	Treatment Period										FU Period	Notes:
		Main Study					Extension Study						
Study Day		1 ²											
Study Weeks	-12 to 0		4 ³	8 ⁴	12 ³	16 ⁴	24 ³	26 ⁵	30 ⁴	38 ³	48 ³	ET ^{3,6}	51 ⁷ /EOS
Visit window (days)			±2	±7	±7	±7	+7	+7	±7	±14	+14		±14
Complete physical exam	X ^d					X			X				d. includes recording height, weight, and calculating BMI.
Limited physical assessment ^e		B	X	X	X	X		X	X		X		e. if clinically indicated. May be performed by home health nurse for remote visits.
Body weight	X	B		X		X			X	X	X		The Investigator will be requested to further evaluate subjects with weight loss of $\geq 15.0\%$ at Week 12 and $\geq 20.0\%$ at Week 24, from baseline, for the potential cause of weight loss.
Waist and hip circumference	X	X		X		X			X	X	X		
Lifestyle counseling	X	X	X	X	X	X	X	X	X				Strenuous exercises should be avoided for at least 48 hours prior to study visits.
Fibroscan VCTE and CAP	X ^f					X			X	X			f. Fibroscan should ideally be performed prior to MRI-PDFF. At Screening, a historical Fibroscan assessment performed within the last 3 months prior to screening may be acceptable.
12-lead ECG (single) ^g	X	B		X		X			X	X	X		g. ECGs will be recorded as single bedside measurements. Additional ECG may be conducted if clinically indicated. ECG should be performed prior to vital signs and laboratory assessments. All ECG data should be provided within 72 hours to the central reader for assessment.
Urine drug screen	X ^h												h. Urine drug screen will be done locally with a standardized kit during screening period by Day 1. If cannot be performed during screening, test can be performed on Day 1, but must be completed before randomization procedures start. Refer to Appendix 2 (Section 10.2).

Assessments	Screening Period ¹	Treatment Period										FU Period	Notes:
		Main Study					Extension Study						
Study Day		1 ²											
Study Weeks	-12 to 0		4 ³	8 ⁴	12 ³	16 ⁴	24 ³	26 ⁵	30 ⁴	38 ³	48 ³	ET ^{3,6}	51 ⁷ /EOS
Visit window (days)			±2	±7	±7	±7	+7	+7	±7	±14	+14		±14
Hematology, and coagulation factors	X	B	X	X	X	X	X	X	X	X	X	X	Refer to Appendix 2 (Section 10.2) for laboratory parameters.
Biochemistry	X ⁱ	B	X	X	X	X	X	X	X	X	X	X	Refer to Appendix 2 (Section 10.2) for laboratory parameters. i. For all subjects, ALT and AST will be collected twice during the Screening period at least 2 weeks apart between the 1 st and 2 nd assessment. A 3 rd assessment, if required, will be collected via unscheduled visit, and performed at least 1 week apart from the 2 nd assessment (refer to Exclusion criterion in Section 5.2.).
FSH	X												Only if required to confirm menopausal status in women under the age of 45 who have amenorrhea >12 months and are not using hormonal contraception or hormone replacement therapy.
LH, FSH, Estradiol		X				X			X				Only for WOCBP who are not on hormonal contraception.
Urinalysis	X	B	X	X	X	X	X	X	X	X	X	X	
HbA1c	X	B		X	X	X		X	X	X	X	X	
HOMA-IR	X	B		X	X	X		X	X	X	X	X	
IGF-1		B		X	X	X		X	X	X	X	X	
Serology	X												Refer to Appendix 2 (Section 10.2) for laboratory parameters (HBsAg, HCV and HIV 1 and 2 antibodies [HCV RNA reflex for HCV Ab+ only]).
Thyroid panel (TSH, FT4, TT3)	X			X	X	X		X	X	X	X	X	
Pregnancy test in WOCBP only ^j	X (Serum)	B	X	X	X	X	X	X	X	X	X	X	j. Serum pregnancy test will be conducted at Screening; at all other timepoints urine pregnancy test will be done. For in-clinic visits at the indicated timepoints, a urine pregnancy test will be

Assessments	Screening Period ¹	Treatment Period										FU Period	Notes:
		Main Study					Extension Study						
Study Day		1 ²											
Study Weeks	-12 to 0		4 ³	8 ⁴	12 ³	16 ⁴	24 ³	26 ⁵	30 ⁴	38 ³	48 ³	ET ^{3,6}	51 ^{7/} EOS
Visit window (days)			±2	±7	±7	±7	+7	+7	±7	±14	+14		±14
Vital signs ^k (blood pressure, pulse, body temperature, and respiratory rate)	X	B	X	X	X	X	X	X	X	X	X	X	obtained locally. If the urine test is positive, dosing should be withheld, a confirmatory serum pregnancy test should be sent to the central laboratory, and the Sponsor should be notified.
Patient reported outcomes		B		B		B			X	X			k. Vital signs will be measured prior to scheduled blood draws. Starting from randomization, blood pressure and pulse will be measured in duplicate, the first measurement will be taken up to 15 minutes before the indicated timepoint. Additional vital signs measurement may be done if clinically indicated. Subjects must be in a supine or semi-erect/seated position and resting for at least 5 minutes prior to measurements. Repeat measurements should be performed according to local practice.
Randomization		X					X ^l						l. for extension study (Placebo QW) At Week 24, subjects randomized to placebo QW in the Main study will be re-randomized 1:1 to pegozafermin 30 mg QW (n=21) or placebo QW (n=21).
Dispense IP		X	<=====X ^m =====>										m. Sponsor-approved courier services may provide IP to subjects from Week 4 through EOS. Depending on geography this may be direct-to-subject shipment or may require site-to-subject shipment. Instructions for dispensation and IP shipment to site and direct-to-subject shipment will be detailed in the Pharmacy Manual. IP should be dispensed approximately every 4 weeks

Assessments	Screening Period ¹	Treatment Period										FU Period	Notes:	
		Main Study					Extension Study							
Study Day		1 ²												
Study Weeks	-12 to 0		4 ³	8 ⁴	12 ³	16 ⁴	24 ³	26 ⁵	30 ⁴	38 ³	48 ³	ET ^{3,6}	51 ^{7/} EOS	
Visit window (days)			±2	±7	±7	±7	+7	+7	±7	±14	+14		±14	
IP administration ⁿ	X	QW from Weeks 1 to 23			QW from Weeks 24 ^o to 47								Dosing window is ±2 days; however for QW dosing, every effort should be made to take IP on the same day of the week and must be at least 5 days between 2 doses. IP will be administered SC to the abdomen by trained and qualified study personnel, site staff at clinic visit(s), or at home by healthcare professional, or subject's caregiver for home administration. IP may also be self-administered at the subject's home. o. Week 26 may be an in-clinic or a remote/home visit by healthcare professional who will administer the IP.	
PK blood collection ^p		B	B	B	B		B			B	X	X		p. PK blood samples will be collected predose. Additional blood samples for PK analysis may be collected if clinically indicated (e.g., in case of SAE). For PK sample collection instruction/procedures, refer to the relevant manual.
ELF panel, Pro-C3, adiponectin, FIB-4 index (derived calculation), and adipo-IR (fasting free fatty acids x fasting insulin)	B			X		X			X	X	X			Refer to Appendix 2 (Section 10.2).
Night-time salivary cortisol (NSC) ^q	X ^q				X		X			X	X	X		q. NSC sample will be collected by subject at home between 8:00pm and 12:00am before submitting the sample for processing at the specified visit. If the sample is not collected between 8:00pm and 12:00am, the test should be repeated. The screening assessment should be performed as early as possible during the screening period. Subjects should be provided with

Assessments	Screening Period ¹	Treatment Period										FU Period	Notes:
		Main Study					Extension Study						
Study Day		1 ²											
Study Weeks	-12 to 0		4 ³	8 ⁴	12 ³	16 ⁴	24 ³	26 ⁵	30 ⁴	38 ³	48 ³	ET ^{3,6}	51 ⁷ /EOS
Visit window (days)			±2	±7	±7	±7	+7	+7	±7	±14	+14		±14
													NSC collection kit at the first screening visit, when possible, to allow sample collection return at the following clinic visit. If screening value is >15 nmol/L, Medical Monitor (or designee) may request further workup should the value be of clinical concern; however, values >15 nmol/L will not be exclusionary. The screening NSC is a safety assessment, and not an I/E criteria. Refer to Section 10.2 for further requirements for values >15 nmol/L on treatment (Section 10.2).
MRI-PDFF	X			X	X				X	X			At Screening, MRI-PDFF should ideally be done before liver biopsy. At Screening, a historical MRI-PDFF assessment performed within the last 3 months prior to screening may be acceptable if the images are available and evaluable by the central imaging vendor. On treatment, MRI-PDFF should ideally be done within ± 7 days of the target visit date. If out of the window, MRI-PDFF should be performed as close to the target visit date.
cT1	X			X	X				X	X			Iron-corrected T1 mapping. Applicable only at sites capable of conducting cT1 imaging. At Screening, a historical cT1 assessment performed within the last 3 months prior to screening may be acceptable if the images are available and evaluable by the central imaging vendor.
Liver/Spleen volume and pancreatic fat	X			X	X				X	X			To be done at the same time as MRI-PDFF. At Screening, a historical liver/spleen volume and pancreatic fat assessment performed within the last 3 months prior to

Assessments	Screening Period ¹	Treatment Period										FU Period		Notes:	
		Main Study					Extension Study								
Study Day		1 ²													
Study Weeks	-12 to 0		4 ³	8 ⁴	12 ³	16 ⁴	24 ³	26 ⁵	30 ⁴	38 ³	48 ³	ET ^{3,6}	51 ^{7/} EOS		
Visit window (days)			±2	±7	±7	±7	+7	+7	±7	±14	+14		±14		
														screening may be acceptable if the images are available and evaluable by the central imaging vendor.	
Bone Mineral Density (BMD) by Dual X Ray Absorptiometry (DXA) ^r		X				X				X	X			r. DXA should be done within -14/+7 days of the target visit date. If out of the window, DXA should be performed as close to the target day as possible.	
Plasma for bone biomarkers analysis		B		X		X				X	X			Includes CTX, P1NP, and osteocalcin; refer to Appendix 2 (Section 10.2).	
Endogenous FGF21 ^s		B												s. Baseline samples of endogenous FGF21 will be obtained in all subjects; additional samples will be obtained at the immunogenicity follow-up visits (See Table 2). Endogenous FGF21 samples (baseline and follow-up visit) will be analyzed only in subjects with neutralizing ADAs.	
Immunogenicity		B	X	X	X		X		X	X ^t	X			t. See Table 2 for immunogenicity follow-up.	
Pharmacogenomic (DNA) blood sampling		X												Optional.	
Blood sample for exploratory biomarkers		X				X			X	X					
Adverse event monitoring ^u	X	X	<=====X=====>						X	X				u. The sites may take non-personally identifying photographs of potential injection site reactions (optional).	
Concomitant medications	X	X	<=====X=====>						X	X					

Abbreviations: ALT, alanine aminotransferase; AST, aspartate aminotransferase; B, predose; CTX, carboxy-terminal collagen crosslinks; D, Day; ECG=electrocardiogram; ELF, enhanced liver fibrosis; EOS, end of study; ET= early termination; FGF21, fibroblast growth factor 21; FIB-4, Fibrosis-4 index; FU, Follow-Up; HbA1c= glycated hemoglobin; HBsAg, hepatitis B surface antigen; HCV, hepatitis C virus; HIV, human immunodeficiency virus; HOMA-IR,

homeostatic model assessment for insulin resistance; I/E, inclusion/exclusion; IGF-1, insulin-like growth factor 1; IP, investigational product; LH, luteinizing hormone; MRI-PDFF, magnetic resonance imaging based proton density fat fraction; NSC, night-time salivary cortisol; P1NP, N-terminal propeptide of type 1 collagen; PK=pharmacokinetic; Pro-C3, N-terminal propeptide of type III collagen; QW, once weekly; Q2W, every 2 weeks; S, serum; TSH, thyroid stimulating hormone; WOCBP=women of child-bearing potential

Table 2: Schedule of Activities (Immunogenicity Follow-up Period)

Assessments	Immunogenicity Follow-up Period				Notes:
	Visit	FU Visit 1	FU Visit 2	FU Visit 3	
Study Week	60	72	84	96	
Visit Window (Days)	± 14	± 14	± 14	± 14	
Immunogenicity ^a	X	X	X	X	
a. Subjects who complete the Week 48 visit will be asked to return to clinic to have blood samples collected approximately every 3 months for up to [REDACTED]. Additional testing may be requested in the event of safety-related concerns. The sponsor may elect to terminate participation in the immunogenicity follow-up period based on emerging data.

Endogenous FGF21 ^b		X		X	
b. Endogenous FGF21 samples will only be analyzed for NAb+ subjects.

Adverse event monitoring ^c	X	X	X	X	
c. Immunogenicity testing for a longer follow-up may be requested in the event of safety-related concerns.

Concomitant medications ^d	X	X	X	X	
d. Changes and new concomitant medication will be recorded.

Abbreviations: FGF21 = fibroblast growth factor 21; FU = follow-up; NAb+ = Neutralizing antibody positive

